6.0 GENERAL CONVENTIONS

Unless otherwise stated, all analyses will be performed using SAS Version 9 and all hypothesis tests will be conducted at a two-sided significance level of 0.05. P-values will be presented with 3 decimals and p-values that are less than 0.001 will be presented as <0.001.

Continuous (non-survival-related) data will be summarized using descriptive statistics: number of observations (n), mean, standard deviation (SD), median, minimum, and maximum. Frequencies and percentages will be used to summarize categorical (discrete) data. Presentations of categorical data will generally suppress percentages for items where the count is zero in order to draw attention to the nonzero counts. In general, mean, standard deviation, median, minimum, maximum, and percentages will be presented with one decimal.

Unless otherwise stated, confidence intervals, when presented, will be constructed at the two-sided 95% level. For binomial variables, the 95% confidence intervals will be constructed using the normal approximation without continuity correction.

Data listings will present all data collected on case report forms (CRFs) by study drug, center, and patient number.

6.1 DEFINITION OF BASELINE

Unless otherwise stated, the last observed measurement before the first dose of CAM2038 will be considered the baseline measurement. If multiple observations are made during baseline, the baseline will be defined as average of the observations obtained during the baseline phase.

6.2 SOFTWARE

Most analyses will be conducted using SAS Version 9.2 or higher.

6.3 CHANGES TO PLANNED ANALYSES

Draft versions of the SAP will be numbered sequentially as Version 0.0i. The final approved version will be numbered as Version 1.00. Revisions after the “Final” version will be numbered as Version 1.0x. The clinical study report will document any changes made after the final version approved before database lock.

7.0 SAMPLE SIZE

A total of 100 patients with at least 48 weeks of CAM2038 exposure will be needed for the safety assessments. Approximately 228 patients will be enrolled initially into this study with an estimated drop-out rate of 50% to ensure a total of 100 patients are exposed to CAM2038. Originally, the study was to end when at least 100 subjects had been exposed to CAM2038 for 12 months (48 weeks). However, a decision was made to allow all enrolled subjects to complete the entire treatment period and to not end the study after at least 100 subjects had completed 48 weeks of treatment.

8.0 DESCRIPTION OF THE STUDY POPULATIONS

All tables, figures, and listings must include a population descriptor (e.g., pre-defined populations: overall safety population, full exposure safety population and efficacy population) in the title.

8.1 DISPOSITION

Patient disposition summaries will be presented and will include the number of patients enrolled, the number and percentage of enrolled patients in each of the pre-defined populations, as well as the number and percentage of patients who complete the study. The summaries will also include the reasons for early discontinuation from the study.

Disposition summaries will be presented for each of the pre-defined populations separately.

8.2 DEMOGRAPHIC AND BASELINE CHARACTERISTICS

A summary of demographics and baseline characteristics will be presented for each of the pre-defined populations. The demographic characteristics will consist of age, sex, ethnicity, and race using descriptive statistics.

Demographic data including age, race, ethnicity, and gender, as well as baseline clinical characteristics will be summarized. Age will be calculated based on the following conditional algorithm:

- Has the patient had his/her birthday this year?

- Yes, then AGE = (year of informed consent) – (year of birth).
- No, then AGE = (year of informed consent) – (year of birth) – 1.

Clinical baseline characteristics summarized will include, if available, weight, body mass index, region (Europe, the US and Australia), type of primary opioid use, years of drug use, when first diagnosed with opioid dependence, proportion of patients previously treated for opioid dependence and duration of buprenorphine treatment.

8.3 MEDICAL HISTORY

Medical history will be coded using the Medical Dictionary for Regulatory Activities (MedDRA). Medical history will be summarized and listings will be presented.

9.0 PRIOR AND CONCOMITANT MEDICATIONS

All medications recorded on the CRFs will be coded using the WHO DRUG Dictionary. Prior and concomitant medications will be summarized by anatomical therapeutic chemical (ATC) Class Level 4 and WHO Drug base substance preferred name.

Prior medications are defined as medications with stop dates occurring before the date of the first administration of any study treatment component. Concomitant medications are defined as medications with start dates occurring on or after the date of the first administration of any study treatment component and no more than 30 days after the last administration of any study treatment component. Medications with start and stop dates that bracket the date of the first administration of any study treatment component will be summarized as both prior and concomitant medications.

Medications that clearly stopped prior to date of the first administration of any study treatment component will be included in the prior medications table, and medications that clearly started on or after date of the first administration of any study treatment component will be included in the concomitant medications table. All other medications will be included in both the prior and concomitant medications tables.

Prior and Concomitant medication will be summarized for the safety populations.

10.0 EFFICACY ANALYSES

10.1.1 EFFICACY VARIABLES

This is a long-term safety study and efficacy evaluation is not the primary objective of the study. All efficacy variables will be summarized using the efficacy population. The efficacy variables will include the following:

- Urine toxicology results for illicit opioids
- Self-reported illicit opioid use
- Retention (%) in treatment (identical to exposure)
- Retention (%) in study
- Measures of opioid withdrawal:
 - Clinical Opiate Withdrawal Scale (COWS)
 - Subjective Opiate Withdrawal Scale (SOWS)

- Measures of opioid craving:
 - Desire to Use Visual Analogue Scale (VAS)
 - Need to Use VAS
- Urine toxicology results for other drugs of abuse
- Work Productivity and Activity Impairment Questionnaire General Health (WPAI-GH)
- EQ-5D-5L Health Questionnaire
- Patient Satisfaction Scale

10.1.2 URINE TOXICOLOGY RESULTS FOR ILLICIT OPIOIDS

Percentage of patients with urine samples negative for illicit opioids (with and without self-reports of illicit opioid use) will be presented by week and month. Mean percentage of urine samples negative for illicit opioids (with and without self-reports of illicit opioid use) will also be presented. Additionally, mean urine samples negative for illicit opioids (with and without self-reports) will be presented by week and month separately for those subjects who were new to treatment upon entry into the study. Due to the flexible visit schedule, no imputation of missing data will be applied.

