5.2. Study Rationale

Opioid drug dependence is a major health and social issue and is often a chronic medical condition that requires long-term maintenance treatment. An important aim of the treatment programs for opioid drug dependence is to enable the patients to become abstinent. Further important aims are to improve their mental and physical health, as well as their social conditions. This can be achieved by increasing patients' quality of life and reducing the burden on the society and relatives. Moreover, opioid people often inject with used syringes and needles, and

thus expose themselves to high risk of transmission of infectious diseases, including HIV and hepatitis C.

Opioid maintenance treatment, such as SL BPN, is one of the most effective treatment options available for opioid dependent drug users and is associated with substantial reductions in deaths, and HIV transmission (WHO, 2004). However, because patients often discontinue treatment prematurely, an outcome associated with higher rates of relapse to drug use, treatment strategies that aim to keep patients in treatment longer and/or improve patient adherence may have additional advantages (Chandler et al, 2009). While daily dosing with SL BPN has proven effective, the need for daily administration of treatment may negatively influence patients' compliance. Moreover, SL tablets or film can be easily diverted for illicit use, injected for greater effect, or accidentally ingested, especially by children (Chandler et al, 2009; Winstock et al, 2008). The limitations associated with SL BPN are of particular relevance to patients who have children at home, to those who have difficulty making frequent visits to the physician's office (e.g., patients in remote locations, those with limited mobility, or those who travel frequently) or to those who have difficulty managing the responsibility of daily dosing.

CAM2038 q1w and q4w may increase patient compliance relative to daily SL BPN dosage forms, and may help prevent treatment noncompliance in higher-risk patients (i.e., those patients who take "drug holidays" from their BPN when they wish to abuse illicit opioids). In addition, CAM2038 q1w and q4w may provide significant potential for reducing risks of diversion, abuse, and accidental pediatric exposure, which continue to be important public health consequences of SL BPN therapy.

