7.6. Removal of Subjects from Therapy or Assessment

A subject is free to withdraw his/her consent and discontinue participation in the study at any time for any reason. A subject's participation must therefore be terminated immediately upon his/her request, and the reason(s) for discontinuation appropriately documented.

A subject must be discontinued from the study for any of the following reasons:

- Safety reasons, including AEs or significant concomitant illness, increased concomitant use of recreational drugs, alcohol, psychotropic agents or methadone, injury, or urgent surgeries/procedures that would, in the judgment of the Investigator, affect assessments of clinical status to a significant extent, require discontinuation of study drug, or both
- At the request of the Sponsor, regulatory agency, or Institutional Review Board (IRB)
- Subject is lost to follow-up
- Pregnancy (UK only)
- Death of subject

A subject may also be discontinued from the study, at the discretion of the Investigator and/or Sponsor, for any of the following reasons:

- Subject refuses or is unable to adhere to the study protocol
- Protocol violation
- Pregnancy (in the UK, pregnant subjects must be discontinued, see above)
- Requirement for continual use of opioid analgesics >7 days or requirement for general anesthesia for surgery

The Investigator must maintain a record of all subjects who discontinue from the study prior to completion; the reason(s) for study discontinuation will be documented. In the event that a subject chooses to withdraw from the study, the Investigator should make a reasonable attempt to obtain and record the reason(s) for withdrawal, if possible, although the subject is not obligated to provide such a reason.

All efforts should be made by the Investigator to continue collection of safety assessments at the protocol-defined study visit intervals, including concomitant medications, and AEs in subjects that discontinue study drugs, unless the subject withdraws his/her consent at the time of early discontinuation. The Investigator should also ask the subject to return for the Follow-up assessments, provided that the subject has not withdrawn consent for those assessments. If a subject refuses to complete early termination procedures and/or Follow-up, this information will be recorded.

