9.3.1. Urine Toxicology for Opioids

Urine toxicology samples will be collected at each visit using a urine collection cup containing a temperature sensor. Specimen authenticity will be verified at the site using this sensor to measure

the urine temperature immediately following collection. The temperature of a urine sample within 4 minutes of voiding should fall within the range of 32.2 to 37.7 degrees Celsius (90 to 100 degrees Fahrenheit). If test results are outside these ranges, the subject will be asked to immediately provide another urine sample. If this second sample is outside of the temperature range, the sample will be counted as 'missing', and should not be sent for analysis (any such samples must be documented in the subject's records). A direct observation approach to obtaining urine samples may be used if the Investigator deems it necessary (in Sweden and France, supervision of urine sampling is mandatory). Urine samples will be logged and numbered and then sent to a central laboratory for analysis for the presence of opioids (e.g., morphine and metabolites, oxycodone, hydrocodone, hydromorphone, fentanyl, and methadone). In addition, it is recommended that the scheduled assessment visits take place on Mondays to potentially improve detection of illicit opioid use that may have occurred over the weekend.

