11.4. Determination of Sample Size

A total of 100 subjects with at least 48 weeks of CAM2038 exposure will be needed for the safety assessments. Approximately 228 subjects will be enrolled initially into this study with an estimated dropout rate of approximately 50% to ensure a total of 100 subjects are exposed to CAM2038. Once a total of 100 subjects complete 48 weeks of CAM2038 treatment, the study will be completed.

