10.1.3 SELF-REPORTED ILLICIT OPIOID USE

Percentage of patients reporting no illicit opioid use will be presented by week and month. Mean percentage of reports of no illicit opioid use will also be presented. Due to the flexible visit schedule, no imputation of missing data will be applied.

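### The no-imputation rule for urine and self-report results is justified only for unscheduled visits but also covers dropout and twice-failed samples, so the observed percentage negative can rise if opioid users leave faster

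*SAP*

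**What the plan says.** SAP 10.1.2 plans the percentage of patients with opioid-negative urine by week and month, with and without self-report, and a mean percentage of negative samples. On missing data it says only: "Due to the flexible visit schedule, no imputation of missing data will be applied". SAP 10.1.3 plans the same kind of summary for self-report ("Percentage of patients reporting no illicit opioid use will be presented by week and month") under the same rule. Neither section states a denominator, says whether the mean percentage is averaged per patient or pooled over samples, or plans a sensitivity analysis.

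Four other places bear on which samples will be missing:

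- **Dropout.** SAP 7.0 plans 228 patients "with an estimated drop-out rate of 50% to ensure a total of 100 patients are exposed to CAM2038". It also records the decision to let every enrolled patient finish the treatment period, so late gaps will come mainly from discontinuation rather than study closure.
- **Link between dropout and use.** Protocol 5.2 motivates the study partly "because patients often discontinue treatment prematurely, an outcome associated with higher rates of relapse to drug use".
- **Removal.** Protocol 7.6 includes "increased concomitant use of recreational drugs, alcohol, psychotropic agents or methadone" among the safety reasons for discontinuation, where the investigator judges the effect significant or that study drug must stop. The data it asks sites to keep collecting afterwards are safety assessments, concomitant medications and adverse events; urine toxicology is not named.
- **Failed samples.** Under Protocol 9.3.1, a sample outside the temperature range is repeated at once. "If this second sample is outside of the temperature range, the sample will be counted as" missing, and it is not analysed.

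**The concern.** The reason given for the rule fits only one kind of gap. Under Protocol Table 3, urine is collected weekly on the weekly product and monthly on the monthly product. A monthly patient's empty weeks are therefore not missing data, and imputing them would be wrong. Months after a patient has left, missed scheduled samples and twice-failed samples are different: each may depend on drug use, and the same sentence disposes of them without comment.

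Urine toxicology is the first-named parameter of the secondary objective (Protocol 6.2, SAP 4.1). The study has no comparator, so the course over time in Tables 14.2.1.1 and 14.2.1.2 and Figures 14.2.3 and 14.2.4 is the main efficacy evidence a reader will have. A rise that reflects who stayed could be read as improvement on CAM2038. Retention is tabulated and plotted (SAP 10.1.4 and 10.1.5), but it is not combined with urine status.

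**Working it through.** **The plan's own figure.** The only design figure is the enrolment. One hundred completers at 50% dropout need 100 / (1 − 0.5) = 200 patients. The stated 228 gives 228 × 0.5 = 114 expected completers and a binomial probability of 0.973 of reaching at least 100. The extra patients are an unexplained cushion, not an error. For this point, the figure matters because about half of the patients are expected to give no late urine data.

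**By-month percentage under constant use.** The documents give no negative rate and no dropout rate by urine status, so these are assumed.

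- A share q = 0.40 of patients is always negative and the rest always positive; nobody changes.
- Total dropout by week 48 is 50%. Dropout is exponential, with hazard ratio HR for positive against negative patients.
- Let Rn and Rp be the shares retained, so Rp = Rn^HR, and solve q·Rn + (1 − q)·Rp = 0.50.
- Observed percentage negative = q·Rn / 0.50. Negative and retained, as a share of all dosed = q·Rn.

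| HR | Rn | Rp | Observed at week 48 | Share of all dosed |
|---|---|---|---|---|
| 1 | 0.500 | 0.500 | 40.0% | 20.0% |
| 1.25 | 0.546 | 0.469 | 43.7% | 21.8% |
| 1.5 | 0.583 | 0.445 | 46.6% | 23.3% |
| 2 | 0.638 | 0.408 | 51.1% | 25.5% |
| 3 | 0.711 | 0.359 | 56.9% | 28.4% |

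At HR 2, for example, 0.40x + 0.60x² = 0.50 gives x = 0.638, and 0.40 × 0.638 / 0.50 = 51.1%.

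Other starting values behave the same way. For HR 1 to 3, a constant 60% gives 60.0% to 78.0%, and a constant 80% gives 80.0% to 92.3%. The direction depends on HR: from 60%, the figure falls to 53.5% at HR 0.67 and 48.9% at HR 0.5.

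**Twice-failed samples.** Suppose 60% of samples are truly negative, 1% of negatives are voided, and a share v of positives is voided. The observed percentage is 0.60 × 0.99 / [0.60 × 0.99 + 0.40 × (1 − v)]. That is 60.5% at v = 3%, 61.0% at 5% and 62.3% at 10%. At a constant void rate this moves the level at every visit equally and does not create a trend.

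**Mean percentage.** If it is averaged per patient and use is constant, an always-negative patient scores 100 and an always-positive patient 0 whenever they leave, so the mean stays at 0.40 × 100 = 40%. A simulation with individual negative rates averaging 60% and 50% dropout agrees: the per-patient mean stays at 60.0%. The mean pooled over samples moves to 62.1% when the hazard ratio between a never-negative and an always-negative patient is √3 ≈ 1.73, and to 64.2% when it is 3. The unstated averaging unit therefore decides whether attrition shifts this summary.

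**The case against.** The strongest reply is that efficacy here is exploratory and uncontrolled (Protocol 9.5), summarised descriptively (Protocol 11.3.2), and not the primary objective (SAP 10.1.1). Retention by week is also shown in the same population, so a reader can multiply: at HR 2, 51.1% observed × 50% retained is about 25.5% of all dosed. This stands, and it limits the weight of the point. It does not remove it. The reader would have to know to multiply, and the Efficacy Population (SAP 5.3) already leaves out dosed patients with no post-baseline efficacy data.

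Several stronger readings are tempting, but the documents do not support them.

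- **That the percentage must rise.** It rises only if users leave faster. Protocol 5.2 associates discontinuation with relapse; it does not say that users leave first.
- **That Protocol 7.6 removes patients for opioid-positive urine.** Removal depends on investigator judgment, and the text names recreational drugs, alcohol, psychotropic agents and methadone. A patient removed for increased use has changed use, so the constant-use argument rests on use-related dropout in general. Retained patients with positive urine still count.
- **That failed samples inflate the trend.** Voiding takes two failures, and collection may be observed (in Sweden and France it must be).
- **That a patient leaving early with only negative samples biases the mean percentage.** Under constant use, equal weighting per patient protects that mean. Its limit is that it says nothing about the time after exit.
- **That observed and conservative figures bracket the truth.** With half the patients missing, an observed 70% is compatible with 0.5 × 70 = 35% up to 35 + 50 = 85%.

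**Conclusion.** The concern holds in a limited form. The stated reason for not imputing covers unscheduled weeks only, while the rule also drops post-discontinuation months and twice-failed samples, and no sensitivity analysis shows how much this matters. With 50% dropout and a constant 40% negative, the late observed figure could be unchanged (HR 1), about 7 points high (HR 1.5), 11 points high (HR 2) or 17 points high (HR 3), and it would be low if users stayed longer. The starting rate and hazard ratios are assumed, dropout is taken as exponential, and the denominator is taken to be patients with a result at that time. This last is the natural reading of the rule, but the SAP does not state it. Over the whole Efficacy Population the percentage would fall with dropout instead.

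The point affects the interpretation of a secondary descriptive result. It does not touch the primary safety objective. The change is cheap and worth making.

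**What to change.** In SAP 10.1.2 and 10.1.3:

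1. Keep the observed-data tables and show the number of patients contributing at each time point.
2. State the denominator, and whether the mean percentage is averaged per patient or pooled over samples. State also how a month with several weekly samples is classified.
3. Add a by-month companion to Tables 14.2.1.1, 14.2.1.2 and 14.2.3.1 with all dosed patients as denominator. Count months after discontinuation, missed scheduled samples and twice-failed samples as not negative. For self-report, do not count a missing report as a report of no use.
4. Define expected samples by the regimen in force, so that weeks without a scheduled visit on the monthly product are never imputed.
5. For Tables 14.2.2.1 and 14.2.2.2, which are not by time, add an overall version with each patient's expected samples as denominator.
6. Label the two sets observed and conservative, not upper and lower bounds.

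The cost is SAP wording and about five more tables. The conservative figure will be less favourable by construction: in the table above it is 20% to 28% although the true constant rate is 40%, so it should not be read as an estimate. Protocol 9.3.1 requires failed samples to be documented in the subject's records, so someone must check that they can be identified in the database.

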10.1.3 SELF-REPORTED ILLICIT OPIOID USE

Percentage of patients reporting no illicit opioid use will be presented by week and month. Mean percentage of reports of no illicit opioid use will also be presented. Due to the flexible visit schedule, no imputation of missing data will be applied.

